11.4 Non-biomarker subgroup analyses

PFS, ORR, DoR, and OS will be reported for the following subgroups. All analyses will be conducted using the FAS based on both IRC and INV response assessment. Kaplan-Meier curves will be provided for PFS, DoR, and OS. For PFS and OS analyses, the estimate of the hazard ratio and corresponding 95% CI will be calculated using a Cox proportional hazards model with only one covariate in the model.

- Gender (Male vs. Female)
- RTX refractoriness (yes vs. no; see section 8.7.4.1.3)
- Refractoriness to last prior treatment line (yes vs. no; see section 8.7.4.1.2)
- Primary refractoriness (yes vs. no; see section 8.7.4.1.1)
- Prior autologous stem cell transplantation (yes vs. no)
- NHL subtype as per central pathology (dichotomized, i.e., DLBCL patients vs. non-DLBCL patients)
- Number of prior treatment lines (1 vs. ≥ 2)
- Number of prior treatment lines (1 vs. 2 vs. 3 vs. 4)
- Reason for ASCT ineligibility:
 - Chemorefractory

-
- High age or Comorbidities
 - Other

12. DESCRIPTIVE BIOMARKER ANALYSES

Biomarker assessments will be tabulated by descriptive statistics. Summaries will be provided for the following variables:

- CD16 molecules on CD16⁺CD56⁺ NK cells (continuous variable)
- Percentage specific killing (ADCC assay) (continuous variable)
- FcγRIIIa affinity (categorical variable):
 - 2 subgroups (high affinity: FCGR3A-158V homozygosity vs. low affinity: FCGR3A-158F homozygosity, or FCGR3A-158F/V heterozygosity).
 - 3 subgroups (FCGR3A-158V homozygosity vs. FCGR3A-158F homozygosity vs. FCGR3A-158F/V heterozygosity).
- FcγRIIa affinity (categorical variable):
 - 2 subgroups (high affinity: FCGR2A-131H homozygosity vs. low affinity: FCGR2A-131R homozygosity, or FCGR2A-131H/R heterozygosity).
 - 3 subgroups (FCGR2A-131H homozygosity vs. FCGR2A-131R homozygosity vs. FCGR2A-131H/R heterozygosity).
- NK cell numbers at baseline (continuous and categorical variable):
 - NK cell numbers/μl at baseline (continuous variable).
 - Baseline and demographics characteristics as described in Section 8.5 will be shown for both subgroups defined by NK cell numbers/μl at baseline less than the median and above or equal to the median.
- Longitudinal analyses will be conducted for: Peripheral numbers of NK cells, B cells, and T cells (analysed separately):
 - Summary statistics per visit (a 95% confidence interval for the median will be derived by bootstrapping)
 - Relative change from baseline (a 95% confidence interval for the median will be derived by bootstrapping).
 - Graphical illustration showing individual values for both absolute values and separately relative change from baseline. The median across all patients (without confidence interval) will be shown.

-
- Graphical illustration showing the median and its 95% confidence interval (via bootstrapping) for both absolute values and relative change per visit across all patients assessed.
 - Graphical illustration showing boxplots for both absolute values and relative change per visit across all patients assessed.
 - Cell of origin (categorical variable):
 - Cell of origin determined by immuno-histochemistry (IHC) assessment (i.e., central pathology): *germinal center B cell (GCB)* phenotype vs. *non-GCB* phenotype.
 - Cell of origin determined by gene expression profiling (GEP): *GCB* phenotype vs. *activated B cell (ABC)* phenotype vs. *unclassified* phenotype.
 - A Listing will be provided showing the information on double hit status (genetic lesions in BCL-2 and MYC as assessed by FISH), and triple hit status (genetic lesions in BCL-2, MYC, and BCL-6 as assessed by FISH). Only those patients will be listed who have been assessed.

Concordance between cell-of-origin determination by gene expression profiling and immuno-histochemistry

The concordance rate represents the agreement regarding the cell-of-origin as determined by gene expression profiling (GEP) and immuno-histochemistry (IHC). The concordance rate is the number of patients that are concordant over the total number of patients assessed, and will be calculated across all cell-of-origin categories. The concordance rate will be calculated using the following categories:

Analysis 1: ABC (GEP) and GCB (GEP) vs. Non-GCB (IHC) and GCB (IHC).

Analysis 2: (ABC (GEP) + Unclassified (GEP)) and GCB (GEP) vs. Non-GCB (IHC) and GCB (IHC).

A confusion matrix (i.e., a contingency table with GEP cell-of origin as rows and IHC cell-of origin as columns) will be generated. The concordance rate will be calculated by adding the diagonal counts and dividing by the total number of patients assessed.

As only a fraction of patients have undergone GEP and IHC analysis, only those patients will be considered for the concordance analysis who have been evaluated by both assessments (i.e., GEP and IHC). Considered for the concordance analysis are only patients from the FAS.

Listings will be provided for all biomarkers (both baseline values and, if applicable, results of subsequent assessments).

All descriptive analysis of biomarkers will be performed using the FAS. Listings will be generated showing individual data on the biomarkers.

13. ADDITIONAL SAFETY ANALYSES

13.1 Adverse events

The analysis of adverse events is comprehensively described in Section 10.7.

13.2 Vital signs

13.2.1 Vital signs variables

The Vital Signs captured in the eCRF for each patient at each visit are the following:

- Weight (all visits)
- Height (only Screening Visit)
- Systolic Blood Pressure (all visits)
- Diastolic Blood Pressure (all visits)
- Heart Rate (all visits)
- Respiratory Rate (all visits)
- Temperature (all visits)
- Overall interpretation of Vital Signs (all visits)

13.2.2 Vital signs analysis

The following analysis will be performed on these variables:

- i. These variables will be summarized by visit by means of descriptive statistics of actual values and change from baseline.
- ii. Overall interpretation of Vital Signs will be tabulated to present the corresponding frequency count and percentage at each visit.
- iii. The normal ranges for the vital sign variables are:
 - Systolic blood pressure: 70-149 mm Hg
 - Diastolic blood pressure: 60-90 mm Hg
 - Heart rate: 55-110 beats per minute
 - Respiratory rate: 10-24 breaths per minute
 - Body temperature: 36.1-37.8 °C (97.0-100.0 °F)

Vital Signs will be listed by visit for the SAF and an abnormal value will be flagged to show whether it is a value below or above the normal limit.

The analysis will be performed on the SAF.

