6.1 MOR00208

MOR00208 will be centrally supplied. MOR00208 drug product (DP) must be stored under refrigeration at 2° C to 8° C in its original package in an appropriate storage facility accessible only to the pharmacist(s), the investigator, or a duly designated person.

MOR00208 DP is a yellowish lyophilisate supplied in single-use 20 mL glass vials. Each vial contains 200 mg of MOR00208 for reconstitution with 5 mL water for injection (WFI). Reconstitution yields 40 mg/mL MOR00208 in 25 mM sodium citrate, 200 mM trehalose and 0.02% (w/v) polysorbate 20 at pH 6.0. Each product vial is intended to deliver 200 mg of MOR00208 in 5 ml of reconstituted solution. The solution after reconstitution is colourless to slightly yellow and essentially free of foreign particles; it may contain a few white to whitish product-related particles.

For administration, MOR00208 will be diluted into a commercially available 250 mL infusion container with 0.9% (w/v) sodium chloride for injection.

MOR00208 will be administered IV at a dose of 12.0 mg/kg.

For the first 3 cycles (Cycles 1-3) of the study, each cycle will consist of a MOR00208 infusion on Day 1, Day 8, Day 15 and Day 22 of the cycle. Additionally a loading dose will be administered on Day 4 of Cycle 1. Thereafter MOR00208 will be administered on a bi-weekly (every 14 days) basis with infusions on Days 1 and 15 of each 28-day cycle.

The individual MOR00208 infusion will be prepared under aseptic conditions and administered at the study site, according to the directions of the sponsor, which will be provided in a Drug Preparation Manual. In general, a vial of MOR00208 must be used as soon as possible after reconstitution with WFI. After dilution for infusion, administration of MOR00208 should take place as soon as possible. Maximum allowed storage times and conditions will be detailed in the Drug Preparation Manual.

The preferred procedure for destruction is for all IMPs (including used, partially used, not expired unused and expired unused vials, blisters, boxes or bottles) to be returned to the Drug Depot for destruction.

In case the site is requesting formal approval for destruction of the IMP on site due to local requirements, the local destruction requirements for IMPs described in detail in the Drug Preparation Manual must be fulfilled.

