For the first infusion, the IV infusion rate should be 70 mL/h for the first 30 minutes and subsequently increased to a rate of 125 mL/h; the total infusion duration should ideally not exceed 2.5 hours. All subsequent MOR00208 infusions will be administered IV at a constant rate of 125 mL/h over a 2-hour period. MOR00208 should NOT be administered as an IV push or bolus.

The infusion rate escalation schedules in this protocol and the Drug Preparation Manual are recommendations only. If required, the investigator should use clinical judgement to optimise patient safety by administering the infusion more slowly.

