7.2.8 Vital Signs

Vital signs will be measured at the time points described in the Schedule of Assessments ([Table 5](#)).

These assessments include body temperature, systolic and diastolic blood pressure readings (mmHg), heart rate (beats per minute [bpm]), and respiratory rate (respirations per minute [rpm]). Vital signs will be measured immediately prior to infusion, 15 ± 5 , 30 ± 10 , and then every 60 ± 15 minutes during infusion and at end of infusion (± 20 min). The actual time of vital sign measurements should be accurately documented. If the infusion is interrupted and/or subsequently restarted, vital signs should be assessed every 60 ± 15 minutes after the first hour.

The frequency or the length of the monitoring period may be adapted if clinically indicated, for example if in the opinion of the investigator the vital sign results, at the time of event onset, are clinically significant. In such a case the patient's vital sign measurements should continue to be recorded until they have returned to normal or pre-infusion levels and an AE recorded. If possible, before vital signs are measured, the patient should be resting for at least 5 minutes. The same position should be used each time vital signs are measured for a given patient, and blood pressure should be measured from the arm contralateral to the site of study drug administration. Body temperature should be measured according to normal hospital practice.

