6.12 Selection of data in the event of multiple records in a window

Depending on the statistical analysis method, single values may be required for each analysis window. For example, change from baseline by visit usually requires a single value per visit, whereas a time-to-event analysis would not require one value per analysis window but rather one value for the study.

Unless otherwise noted throughout the rest of this document, when a single value is needed, the following rule(s) will be used:

-
- If more than one assessment occurs during the same nominal visit time window of the planned visit, select the record closest to the nominal day for that particular visit day.
 - If there are two assessments that are equidistant from the nominal planned visit day, the data of the assessment after the scheduled study day will be used.
 - The last measurement will be used if multiple measurements are all taken on the same day.

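### By-visit vital-sign tables default to the last reading of the day, so transient changes during an infusion are left out of the planned summaries

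*SAP*

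**What the plan says.** Protocol section 7.2.8 sets the measurement schedule: "Vital signs will be measured immediately prior to infusion, 15 ± 5 , 30 ± 10 , and then every 60 ± 15 minutes during infusion", with a further reading at the end of the infusion. Protocol section 6.5, on monitoring patients during the MOR00208 infusion, refers to this schedule.

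SAP section 13.2.2(i) gives the analysis: "These variables will be summarized by visit by means of descriptive statistics of actual values and change from baseline". It names no time point within a visit and no worst-value summary. Item (ii) tabulates the overall interpretation per visit. The section also provides a listing with out-of-range values flagged.

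SAP section 6.12 covers visits with several records. It gives change from baseline by visit as its own example of an analysis that usually needs a single value. Where one is needed, and nothing else is specified, "The last measurement will be used if multiple measurements are all taken on the same day". SAP section 6.11 uses the nominal eCRF visit. It adds that parameters including vital signs will be slotted in time if that is indicated, but defines no slots.

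SAP section 6.7 defines the safety baseline as the last assessment on or before the start date of study treatment, excluding post-dose assessments on that day.

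**The concern.** The readings are concentrated in the first half hour and repeated through the infusion, which is when infusion-related reactions are expected to appear. The planned table gives one figure per visit, and the default picks the reading furthest from most of that period. A fall in pressure or a rise in heart rate that has passed by then leaves no trace in the summary.

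This matters because vital signs are one of the safety categories listed under secondary objective 7. Infusion-related reactions were the most common treatment-emergent event in the phase I study of MOR00208 (66.7% of patients, protocol section 1.4.1.1), and 18 of its 27 patients had an infusion paused for one. The notes to Table 1 in protocol section 6.6.1 include hypotension, hypertension and tachycardia among the signs. A reader of the study report would reasonably look to the vital-sign tables for the usual size and timing of these changes.

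**Working it through.** **Infusion length.** The antibody is "diluted into a commercially available 250 mL infusion container" and later infusions are "administered IV at a constant rate of 125 mL/h over a 2-hour period" (protocol section 6.1).
- Later infusions: 250 mL / 125 mL per hour = 2 hours = 120 minutes, which reproduces the protocol's figure.
- First infusion: 30 minutes at 70 mL per hour delivers 35 mL. The remaining 215 mL takes 215 / 125 × 60 = 103 minutes, for a total of 133 minutes. This agrees with the protocol's statement that "the total infusion duration should ideally not exceed 2.5 hours".

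**Readings per infusion.** The 60-minute interval can be counted from the 30-minute reading or from the start.
- 120 minutes: 0, 15, 30, 90, 120, or 0, 15, 30, 60, 120. Five either way. In the second count, the 120-minute reading is also the end reading.
- 133 minutes: five either way, treating a 120-minute reading as the end reading because it falls within the 20-minute tolerance.
- 150 minutes: five or six.

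**Readings per patient, Cycles 1 to 12.** The dosing schedule in SAP section 8.9.1 gives 5 + 4 + 4 + 9 × 2 = 31 infusions.
- Readings required: 31 × 5 = 155.
- Readings used under the last-of-day default: 31 × 1 = 31.
- Readings not used: 155 − 31 = 124, and 124 / 155 = 80%.

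**Which reading is kept.** With no later measurement that day, it is the end-of-infusion reading. If the investigator considers a result clinically significant, protocol section 7.2.8 has measurement continue until values return to normal or to the pre-infusion level. If that happens on the same day and the readings are in the database, the value kept is a recovered one. These are also the cases recorded as adverse events.

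**What it is compared with.** At Cycle 1 Day 1 the study baseline will normally be that day's pre-infusion reading. For the other 31 − 1 = 30 infusions it is not, so drift since the start of treatment is mixed with any effect of the infusion.

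**How the SAP treats comparable data.** MOR00208 concentrations, sampled before and one hour after infusion, are summarised by scheduled sampling time (10.9.3). Laboratory data have worst post-baseline grades and shifts (13.5.3), ECOG status has worst post-baseline shifts (13.6), and ECG has notable-change criteria (13.4.2). Vital signs have neither a time-point summary nor a worst-value summary.

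**The case against.** The strongest reply is that on-infusion changes reach the report by other routes. A clinically significant vital-sign change is recorded as an adverse event (protocol 7.2.8). TEAEs are tabulated by preferred term and grade, and infusion-related reactions of grade 3 or higher have their own row in the overall summary (SAP 10.7). Infusion interruptions are summarised (SAP 16.3.4), and SAP 14.5 promises listings of all collected data. A reader might infer that these changes vanish from the safety results; given these provisions, the documents do not support that. The routes are nevertheless partial. An adverse event gives a term and a grade, not the size or timing of the change, and depends on the investigator's assessment. Flags use fixed limits, so a heart rate rising from 60 to 108 (invented values) stays inside the 55 to 110 range and is not flagged.

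A second reply is that no sentence says one vital-sign value per visit is analysed. The 6.12 rule is conditional, and the slotting sentence in 6.11 also covers PK, which is summarised by time point. That is fair: the single value is the SAP's default, not an explicit statement in 13.2.2. But no slots are defined, and 13.2 notes no exception. If the default were not applied, readings from before, during and after the infusion would be pooled within the visit, which would not show the infusion effect either.

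A third reply is that the end-of-infusion reading may still show a reaction. This stands. The notes to Table 1 in protocol section 6.6.1 say that signs can arise during or shortly after infusion and generally clear within 24 hours of its completion. A reader might infer that any reaction has settled by the last reading; the documents do not say so.

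**Conclusion.** The point holds for the summary tables and for changes that pass before the last reading of the day. Under the SAP's default, about four in five infusion-day readings are not summarised, and the one that is kept is not compared with its own pre-infusion value. The counts assume uninterrupted infusions at the planned rate, all 31 infusions given, no later same-day reading, and use of the 6.12 default.

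No size in mm Hg or beats per minute can be given, because the documents contain no data on vital signs during infusion. A reader might want an estimate of the hidden fall in pressure, but any such figure would only restate what was assumed about the fall and its recovery. Nor does the point extend to the flag limits in 13.2.2, which are a separate clinical choice. It changes no efficacy result and no adverse-event count. It is a weakness in a supporting safety table, worth correcting because the protocol already requires the readings.

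**What to change.** In SAP section 13.2.2(i), for infusion days:
- Summarise vital signs by visit and planned time point (pre-infusion, 15 minutes, 30 minutes, each later 60-minute reading, end of infusion), or by the worst on-infusion value: lowest systolic and diastolic pressure, highest heart rate and temperature.
- In either case, report change from the same-day pre-infusion value.
- Keep change from study baseline for the pre-infusion value.
- State that the last-of-day rule in 6.12 does not apply to vital signs on infusion days.

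The cost is SAP wording, some programming and longer tables; the worst-value version is the shorter one. The sponsor should first confirm that the eCRF holds each time point. SAP section 13.2.1 describes vital signs as captured at each visit without naming time points, and protocol section 7.2.8 does not say that every reading is entered. If some readings exist only in source records, the change would require more than SAP wording.

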13.3 Physical examination

Baseline and End of Treatment full physical examinations will be summarized by body system. New and worsening abnormal physical examination findings during the study will be entered as AEs and analysed within the AE tables. The analysis will be performed on the SAF. Listings on full physical examination will be shown (for the SAF).

13.4 Electrocardiogram (ECG)

13.4.1 ECG variables

The Electrocardiogram variables captured in the eCRF for each patient at each visit are the following:

- QRS Interval
- RR Interval
- PR Interval
- QT Interval
- QTcB: Bazett's correction for QT given by $QTcB = \frac{QT_{max}}{\sqrt{RR}}$, where RR=60/heart rate.
- QTcF: Fridericia's correction for QT given by $QTcF = \frac{QT_{max}}{3\sqrt{RR}}$, where RR=60/heart rate.
- Overall Interpretation of 12 Lead ECG tracing

The variables listed above are not derived by programming, but will be used as entered in the eCRF.

13.4.2 ECG analysis

The following analyses will be performed on these variables:

- i. Overall interpretation of 12 Lead ECG tracing will be tabulated to present the corresponding frequency count and percentage at each visit.
- ii. ECG variables will be summarized by visit by means of descriptive statistics of actual values and change from baseline.
- iii. The normal ranges for the ECG variables are:
 - PR interval: 110-220 ms
 - QRS interval: 60-120 ms
 - RR interval: 600-1200 ms
 - QT interval (also corrected): ≤ 400 ms
- iv. As recommended in the FDA guidance E14 on Clinical Evaluation of QT/QTc interval prolongation and Proarrhythmic Potential for Non-Antiarrhythmic Drugs (October 2015), the number and percentage of patients having notable ECG interval values will be as follows in Table 15.

**Table 15: Clinically notable ECG values**

ECG parameter (unit)	Clinically notable criteria
QTcF (ms)	New > 450 ms New > 480 ms New > 500 ms Increase from Baseline > 30 ms Increase from Baseline > 60 ms
PR duration (ms)	Increase > 25% from Baseline and to PR duration > 200 ms
QRS duration (ms)	Increase > 25% from Baseline and to QRS duration > 110 ms

- v. All assessments will be listed and those collected outside of the treatment window will be flagged.

The summaries will include only assessments on treatment. The analysis will be performed on the SAF. Listings on ECG interpretation and ECG intervals will be shown.

13.5 Laboratory data

13.5.1 Laboratory variables

Laboratory parameters measured in the central laboratory can be separated into

- Blood parameters (haematology, serum chemistry, coagulation).
- Urine parameters (urinalysis).

